**Figure 1. Cohort Enrollment**

WAIHA = warm autoimmune hemolytic anemia

**Table 2. Study Assessments for Cohort 1**

	Screening	Treatment Period										Follow-Up						
Visit Number	1	2	3	4	5	6	7	8	9	10	11	12	13	14	15	16	17	18 (or ET)
Time Point (Study Day)	-14 to -1	0	1 (±1 h)	2 (±2 h)	5 a (±4 h)	7 (±6 h)	12 a (±6 h)	14 (±6 h)	19 a (±6 h)	21 (±6 h)	28 (±6 h)	29 (±1 h)	30 (±2 h)	33 (±4 h)	42 (±3 d)	56 (±5 d)	84 (±5 d)	112 (±5 d)
Informed consent	X																	
Demographics/medical history	X																	
Inclusion/exclusion	X																	
Physical examination b	X	X				X		X		X	X				X	X	X	X
Vital signs c	X	X	X	X	X	X	X	X	X	X	X	X	X	X	X	X	X	X
Karnofsky Performance Scale	X																	
Pulse oximetry d		X				X		X		X	X							
Clinical safety labs e	X	X				X		X		X	X			X	X	X	X	X
Pregnancy test f	X	X														X		X
Hepatitis and HIV antibody screen	X																	
12-lead ECG g	X	X					X				X					X		
Tetanus and VZV antibodies h		X														X	X	X
Cold agglutinins (titer and thermal amplitude)		X												X		X	X	X
PK sampling i		X	X	X	X						X	X	X	X				
Immunogenicity j		X						X			X					X	X	X
Study drug administration k		X				X		X		X	X							
Immunoglobulins l	X	X	X	X	X	X	X	X	X	X	X	X	X	X	X	X	X m	X m
CIC		X			X	X	X	X	X	X	X			X	X	X	X	X
Haptoglobin	X	X				X		X		X	X			X	X	X	X	X
Direct Coombs test	X	X						X						X		X	X	X
Additional PD sample collection n		X						X						X		X	X	X
FCGR2A by buccal swab o		X																
RNA sequencing		X						X						X		X	X	X
Urine IgG		X						X						X		X	X	X
Immunophenotyping p		X								X						X		
Quantitative Coombs assay		X						X						X		X		
Adverse events	To be collected from the date that the ICF is signed through the last study visit																	
Concomitant medications	To be collected from within at least 3 months prior to screening through the last study visit																	

CIC = circulating immune complexes; d = day(s); ECG = electrocardiogram; ET = early termination; h = hour(s); *FCGR2A* = Fc gamma R2a receptor; HIV = human immunodeficiency virus; ICF = informed consent form; Ig = immunoglobulin; PD = pharmacodynamic; PK = pharmacokinetic; VZV = varicella-zoster virus.

- a. Visit Days 5, 12, and 19 may be conducted via at-home nurse in lieu of a subject visit to the study site.
- b. Complete **physical examination**, including weight, to be performed. Height and body mass index will be additional assessments conducted at screening.
- c. **Vital sign** measurements (sitting blood pressure, heart rate, respiratory rate, and oral temperature) to be obtained after 5 minutes of seated rest. Any abnormal measurements are to be repeated after 5 minutes of rest. On Days 0, 7, 14, 21, and 28, vital sign measurements will be collected immediately prior to the infusion; 15, 30, and 45 minutes after the start of the infusion; at completion of the infusion; and 30 minutes, 1 hour, and 2 hours following completion of the infusion.
- d. **Pulse oximetry**: On Days 0, 7, 14, 21, and 28, pulse oximetry to be measured immediately prior to the infusion; 15, 30, and 45 minutes after the start of the infusion; at completion of the infusion; and 30 minutes, 1 hour and 2 hours following completion of the infusion.
- e. **Clinical safety labs**: hematology, clinical chemistry, and urinalysis. See [Section 6.7](#) for a complete list. Full clinical safety laboratory draws will be collected at screening and on Days 0, 7, 14, 21, 28, 33, 42, 56, 84, and 112. PD markers (albumin levels, hematocrit, hemoglobin, platelet count, reticulocyte count, lactate dehydrogenase, and total and indirect bilirubin) will be derived from the clinical safety laboratory results.
- f. **Pregnancy test (women of childbearing potential only)**: To be performed at time of screening, prior to first dose of SYNT001 on Day 0, and on Days 56 and 112. Urine or serum test is acceptable; however, positive urine tests must be confirmed with serum testing.
- g. Digital 12-lead **ECG** to be obtained in triplicate at least 1 to 2 minutes apart and after 5 minutes of rest in a supine position. See [Section 6.6](#) for additional information. On Days 0 and 28 to be obtained 5 minutes after the completion of infusion. Day 12 ECG will be collected only if the visit is conducted at the study site.
- h. **Serology**: Testing at Day 56 will not be done for any subject whose baseline titer is below the level of detection. If the Day 56 results are greater than 30% below the baseline value, or if the subject falls below the level of detection, the subject will be re-tested at Day 84; if still below the baseline value (or level of detection), the subject will be re-tested at Day 112. Any subject whose baseline value for tetanus or VZV was above the detectable level at baseline and is not within 30% of the baseline value or is below the detectable level by Day 112, will be referred to their primary care physician for further management. See [Section 6.7.3](#) for additional information.
- i. **PK**: Starting on Days 0 and 28, serum samples will be collected just prior to the start of study drug infusion (pre-dose), and at 5 minutes and 2, 4, 6, 24, and 48 hours after the end-of-study drug infusion. Additional samples will be collected on Days 5 and 33. See [Section 6.7.4](#) for additional information.
- j. **Immunogenicity**: Blood samples will be collected pre-dose when collected on dosing days. Samples will be collected on Days 0, 14, 28, 56, 84 and 112. See [Section 6.7.6](#) for additional information.
- k. Prior to **study drug infusion**, SYNT001 drug product is to be diluted in dextrose 5% in water to a total volume of 250 mL and administered intravenously over 1 hour  $\pm$ 15 minutes using a 0.2-micron, inline filter. See [Section 9](#) for additional information.
- l. **Immunoglobulins (IgG, IgA, IgM) and IgG subtypes (IgG1-4)**: Collected for measurements of IgG, IgG subtypes (IgG1-4), IgA, IgM at every visit. On Days 0, 7, 14, 21, and 28, samples are collected prior to infusion of study drug.
- m. Subjects will return to the clinic on Days 84 and 112 for follow-up visits. Subjects whose total IgG is not within 30% of their Day 0 baseline value and not above 500 mg/dL at the Day 112 visit will be referred for further management.
- n. **Additional PD samples** to be collected for measurements of biomarkers, including D-dimer; antiphospholipid antibodies (lupus anticoagulant, anti-cardiolipin, and anti-beta-2-GP1 antibodies); antinuclear antibody titer; anti-double-stranded DNA antibody titer; complement component 3. See [Section 6.7.5](#) for complete information.
- o. Buccal samples to be collected and stored.
- p. **Immunophenotyping** by flow cytometry for measurement of CD3+CD4+ T, CD3+CD8+ T, monocytes, natural killer (NK) cells, and B cells

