- b. **Vital sign** measurements (sitting blood pressure, heart rate, respiratory rate, and oral temperature) to be obtained after 5 minutes of seated rest. Any abnormal measurements are to be repeated after 5 minutes of rest. Vital sign measurements will be taken on all study visits. On dosing days, vital sign measurements will be collected immediately prior to the infusion; 15, 30, and 45 minutes after the start of the infusion; at completion of the infusion; and 30 minutes, 1 hour and 2 hours following completion of the infusion.
- c. **Pulse oximetry**: On dosing day, pulse oximetry to be measured immediately prior to the infusion; 15, 30, and 45 minutes after the start of the infusion; at completion of the infusion; and 30 minutes, 1 hour, and 2 hours following completion of the infusion.
- d. **Clinical safety labs**: hematology, clinical chemistry, and urinalysis. See Section 6.7 for a complete list. Full clinical safety lab draws will be collected at screening and at all study visits prior to infusion if applicable. PD markers (albumin levels, hematocrit, hemoglobin, platelet count, reticulocyte count, lactate dehydrogenase, and total and indirect bilirubin) will be derived from the clinical safety laboratory results.
- e. **Pregnancy test (women of childbearing potential only)**: To be performed at time of screening and prior to dose on dosing days if applicable. Urine or serum test is acceptable; however, positive urine tests must be confirmed with serum testing.
- f. Digital 12-lead **ECG** to be obtained after 5 minutes of rest in the supine position and in triplicate approximately 1 minute apart. See Section 6.6 for additional information. On days of treatment, to be obtained 5 minutes after the completion of infusion.
- g. **Serology**: Any subject whose baseline value for tetanus or VZV was above the protective level at baseline and is not within 30% of the baseline value or is below the protective level by End of Follow-up, will be referred to their primary care physician for further management. See Section 6.7.3 for additional information.
- h. **PK**: Starting on dosing days, serum samples will be collected just prior to the start of study drug infusion (pre-dose) and at 5 minutes, 1 and 2 hours after the end of study drug infusion. See Section 6.7.4 for additional information.
- i. **Immunogenicity**: Samples will be collected pre-dose when collected on dosing days. See Section 6.7.6 for additional information.

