### 6.7.3 Serum Tetanus Antibody and Varicella-Zoster Virus Antibody Testing

Samples for serum tetanus antibody and Varicella-Zoster virus antibody testing are to be collected. Any subject whose baseline value for tetanus or VZV was above the protective level at baseline and is not within 30% of the baseline value or is below the protective level by the end-of-study visit, will be referred to their primary care physician for further management.

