- Complete physical exam ([Section 6.3](#))

- Vital sign measurements (after 5 minutes of rest; sitting blood pressure, heart rate, respiratory rate, oral temperature): abnormal results to be repeated after 5 minutes of rest ([Section 6.5](#))
- Clinical safety laboratory tests (hematology, serum chemistry panel, urinalysis) ([Section 6.7](#))
- PD sample collection ([Section 6.7](#))
  - IgG, IgG subtypes (IgG1-4), IgA, IgM and CIC
  - Haptoglobin
- Concomitant medication assessment ([Section 6.10](#))
- AE assessment ([Section 6.9](#))

#### 7.1.16 Follow-up: Day 56

On Day 56 ( $\pm$  5 days), subjects are to return to the clinic and the following procedures are to be performed:

- Complete physical examination ([Section 6.3](#))
- Vital sign measurements (after 5 minutes of rest; sitting blood pressure, heart rate, respiratory rate, oral temperature): abnormal results to be repeated after 5 minutes of rest ([Section 6.5](#))
- Clinical safety laboratory tests (hematology, serum chemistry panel, urinalysis) ([Section 6.7](#))
- Pregnancy test ([Section 6.7](#))
- 12-Lead ECG (to be obtained in triplicate at 5 minutes after the completion of study drug infusion ([Section 6.6](#)))
- Serum tetanus antibody and VZV antibody; testing at Day 56 will not be done for any subject whose baseline titer is below the level of detection. See [Section 6.7.3](#) for additional information.
- Immunogenicity sample collection ([Section 6.7](#))
- PD sample collection ([Section 6.7](#))
  - IgG, IgG subtypes (IgG1-4), IgA, IgM and CIC
  - Haptoglobin
  - Direct Coombs test
  - D-dimer
  - Antiphospholipid antibodies (lupus anticoagulant, anti-cardiolipin, and anti-beta-2-GP1 antibodies)
  - ANA and anti-dsDNA antibody titers
  - C3
  - Cold agglutinins (titer and thermal amplitude)
  - Quantitative Coombs assay
  - Exploratory biomarkers (RNAseq, urine IgG)
  - Immune phenotyping by flow cytometry for measurement of CD3+CD4+ T, CD3+CD8+ T, monocytes, NK cells and B cells
- Concomitant medication assessment ([Section 6.10](#))
- AE assessment ([Section 6.9](#))

### 7.1.17 Follow-up: Day 84

On Day 84 ( $\pm$  5 days), subjects are to return to the clinic and the following procedures are to be performed:

- Complete physical examination ([Section 6.3](#))

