- Vital sign measurements (after 5 minutes of rest; sitting blood pressure, heart rate, respiratory rate, oral temperature): abnormal results to be repeated after 5 minutes of rest ([Section 6.5](#))
- Clinical safety laboratory tests (hematology, serum chemistry panel, urinalysis) ([Section 6.7](#))
- Serum tetanus antibody and VZV antibody if required. See [Section 6.7.3](#) for additional information.
- Immunogenicity sample collection ([Section 6.7](#))
- PD sample collection ([Section 6.7](#))
  - IgG, IgG subtypes (IgG1-4), IgA, IgM and CIC
  - Haptoglobin
  - Direct Coombs test
  - D-dimer
  - Antiphospholipid antibodies (lupus anticoagulant, anti-cardiolipin, and anti-beta-2-GP1 antibodies)
  - ANA and anti-dsDNA antibody titers
  - C3
  - Cold agglutinins (titer and thermal amplitude)
  - Exploratory biomarkers (RNAseq, urine IgG)
- Concomitant medication assessment ([Section 6.10](#))
- AE assessment ([Section 6.9](#))

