### 7.1.18 Follow-up: Day 112 (End of Study) or Early Termination Visit

On Day 112 ( $\pm$  5 days), subjects are to return to the clinic and the following procedures are to be performed:

- Complete physical examination ([Section 6.3](#))
- Vital sign measurements (after 5 minutes of rest; sitting blood pressure, heart rate, respiratory rate, oral temperature): abnormal results to be repeated after 5 minutes of rest ([Section 6.5](#))
- Clinical safety laboratory tests (hematology, serum chemistry panel, urinalysis) ([Section 6.7](#))
- Pregnancy test ([Section 6.7](#))
- Serum tetanus antibody and VZV antibody; testing if required. See [Section 6.7.3](#) for additional information.
- Immunogenicity sample collection ([Section 6.7](#))
- PD sample collection ([Section 6.7](#))
  - IgG, IgG subtypes (IgG1-4), IgA, IgM and CIC
  - Haptoglobin

- Direct Coombs test
- D-dimer
- Antiphospholipid antibodies (lupus anticoagulant, anti-cardiolipin, and anti-beta-2-GP1 antibodies)
- ANA and anti-dsDNA antibody titers
- C3
- Cold agglutinins (titer and thermal amplitude)
- Exploratory biomarkers (RNAseq, urine IgG)
- Concomitant medication assessment ([Section 6.10](#))
- AE assessment ([Section 6.9](#))

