- h. Serology: Testing at Day 56 will not be done for any subject whose baseline titer is below the level of detection. If the Day 56 results are greater than 30% below the baseline value, or if the subject falls below the level of detection, the subject will be re-tested at Day 84; if still below the baseline value (or level of detection), the subject will be re-tested at Day 112. Any subject whose baseline value for tetanus or VZV was above the detectable level at baseline and is not within 30% of the baseline value or is below the detectable level by Day 112, will be referred to their primary care physician for further management. See Protocol Section 6.7.3 for additional information.
- i. PK: Starting on Days 0 and 28, serum samples will be collected just prior to the start of study drug infusion (pre-dose), and at 5 minutes and 2, 4, 6, 24, and 48 hours after the end-of-study drug infusion. Additional samples will be collected on Days 5 and 33. See Protocol Section 6.7.4 for additional information.
- j. Immunogenicity: Blood samples will be collected pre-dose when collected on dosing days. Samples will be collected on Days 0, 14, 28, 56, 84 and 112. See Protocol Section 6.7.6 for additional information.
- k. Prior to study drug infusion, SYNT001 drug product is to be diluted in dextrose 5% in water to a total volume of 250 mL and administered intravenously over 1 hour ±15 minutes using a 0.2-micron, inline filter. See Protocol Section 9 for additional information.
- l. Immunoglobulins (IgG, IgA, IgM) and IgG subtypes (IgG1-4): Collected for measurements of IgG, IgG subtypes (IgG1-4), IgA, IgM at every visit. On Days 0, 7, 14, 21, and 28, samples are collected prior to infusion of study drug.
- m. Subjects will return to the clinic on Days 84 and 112 for follow-up visits. Subjects whose total IgG is not within 30% of their Day 0 baseline value and not above 500 mg/dL at the Day 112 visit will be referred for further management.
- n. Additional PD samples to be collected for measurements of biomarkers, including D-dimer; antiphospholipid antibodies (lupus anticoagulant, anti-cardiolipin, and anti-beta-2-GP1 antibodies); antinuclear antibody titer; anti-double-stranded DNA antibody titer; complement component 3. See Protocol Section 6.7.5 for complete information.
- o. Buccal samples to be collected and stored.
- p. Immunophenotyping by flow cytometry for measurement of CD3⁺CD4⁺ T, CD3⁺CD8⁺ T, monocytes, natural killer (NK) cells, and B cells.

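### Cohort 1 tetanus and VZV follow-up turns on the detectable level in Table 2 footnote h but on the protective level in Section 6.7.3, so a subject who loses protection with a fall of 30% or less may get no retest or referral

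*Protocol*

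**What the plan says.** **Cohort 1.** Protocol Table 2 footnote h, repeated in SAP Appendix A Table 2, works in steps.

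- Gate: a subject with an undetectable baseline titre is not tested at Day 56. Section 7.1.16 repeats this: "testing at Day 56 will not be done for any subject whose baseline titer is below the level of detection".
- Day 84 retest: required if the Day 56 titre is more than 30% below baseline, "or if the subject falls below the level of detection, the subject will be re-tested at Day 84".
- Day 112 retest: follows a Day 84 retest, "if still below the baseline value (or level of detection), the subject will be re-tested at Day 112".
- Referral: a subject detectable at baseline who is not within 30% of baseline, or who "is below the detectable level by Day 112, will be referred to their primary care physician".

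The visit sections make the later draws conditional. Section 7.1.17 (Day 84) has "Serum tetanus antibody and VZV antibody if required" and Section 7.1.18 (Day 112) has "Serum tetanus antibody and VZV antibody; testing if required". Both then point to Section 6.7.3.

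**Section 6.7.3.** This section names no cohort, and footnote h refers to it. It covers subjects above the protective level at baseline. It refers anyone who is not within 30% of baseline or who "is below the protective level by the end-of-study visit, will be referred to their primary care physician". It contains no retest rule.

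**Cohort 2.** Footnote g in Protocol Tables 3 and 10 and in SAP Tables 3 and 4 follows 6.7.3: a subject protected at baseline is referred if not within 30% of baseline or if the titre "is below the protective level by End of Follow-up, will be referred to their primary care physician". Section 7.2.6 draws the Day 91 and Day 140 titres without any condition.

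No numerical value is given for either the detection limit or the protective level of either antibody.

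**The concern.** Section 9.6.3 of the Protocol names loss of vaccine-derived protection as a possible effect of SYNT001 and says that protective levels will be tested under 6.7.3. A detectable titre need not be a protective one. Two rules with different absolute limits therefore apply to the same Cohort 1 subject, and no text says which governs.

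The choice of limit matters most for a subject who was protected at baseline and whose fall is too small for the 30% limb to act. That situation is plausible at Day 56, which is 28 days after the last Cohort 1 dose (56 − 28). Section 9.6.3 describes total IgG returning to within 30% of baseline within 4 weeks, after one dose in volunteers and after multiple doses in non-human primates. Section 2.2 reports return to baseline within 1 to 2 months in pemphigus patients on five weekly doses of 10 mg/kg. These figures are for total IgG, not for specific titres. They show only that the 30% limb may not be met at Day 56, which leaves the absolute limit to decide.

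At stake is a safety referral to primary care, and the Day 84 titre that would show whether the deficit persists.

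**Working it through.** The plan gives no figure to reproduce. The check is to write both rules in the same units and find where they disagree.

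**Notation.** Set the protective level to 1. Let b be the baseline titre and f the fall from baseline, so that the later titre is x = b(1 − f). Let r be the detection limit as a multiple of the protective level. The documents do not give r, so it is an assumption and is varied below. Only falls are considered.

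**The rules.**

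- Footnote h, for b above r: retest and refer if f > 0.30 or x < r.
- Section 6.7.3, for b > 1: refer if f > 0.30 or x < 1.

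**Reached by 6.7.3 only.** This needs b > 1, f ≤ 0.30 and r ≤ x < 1.

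- x < 1 means f > 1 − 1/b.
- Together with f ≤ 0.30 this requires 1 − 1/b < 0.30, that is b < 1/0.70 = 1.43.
- x ≥ r means f ≤ 1 − r/b, so the upper end of the window is the smaller of 30% and 1 − r/b.

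For r of 0.7 or less the detection limit does not bind, because b > 1 and f ≤ 0.30 give x > 0.7. The windows are then:

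| Baseline (× protective) | Smallest crossing fall, 1 − 1/b | Largest fall missed by footnote h | Width (points) |
|---|---|---|---|
| 1.1 | 9.1% | 30% | 20.9 |
| 1.25 | 20.0% | 30% | 10.0 |
| 1.4 | 28.6% | 30% | 1.4 |

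**Sensitivity to the detection limit, at b = 1.1.**

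| r | 1 − r/1.1 | Window |
|---|---|---|
| 0.7 | 36.4%, capped at 30% | 9.1% to 30% |
| 0.8 | 27.3% | 9.1% to 27.3% |
| 0.9 | 18.2% | 9.1% to 18.2% |
| 1.0 | 9.1% | empty |

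If the two limits coincide, this gap does not exist.

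**Example.** Take a detection limit of 1 unit, a protective level of 10, a baseline of 12 and a Day 56 titre of 9.5. The fall is (12 − 9.5)/12 = 20.8%. Under footnote h this is not more than 30% and the titre is detectable, so there is no Day 84 retest, hence no Day 112 retest, and no referral. Under 6.7.3 the subject was protected and is now below the protective level.

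**Reached by footnote h only.** Take the same limits with a baseline of 8 and a lasting titre of 5. The fall is (8 − 5)/8 = 37.5%. Footnote h refers this subject. Section 6.7.3 does not, because the baseline was never protective. The same holds for a detectable but unprotected baseline that falls below detection.

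**The case against.** The best reply is that 6.7.3 already covers Cohort 1. It names no cohort, footnote h cites it, and Sections 7.1.17 and 7.1.18 send the site to it. Table 2 also marks the Day 84 and Day 112 draws. A site reading everything together could refer on the Day 56 value. This stands in part: a missed referral is possible, not certain. It does not settle the matter. Section 6.7.3 has no retest trigger, the Table 2 marks carry footnote h, and that footnote holds the only stated condition for a later draw.

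A reader might infer that a single reading of 6.7.3 both requires referral and leaves no end-of-study titre to act on. The text does not support that. If a value at any time up to the end-of-study visit counts, the Day 56 titre is enough and 6.7.3 refers. If an end-of-study value is needed, the rule is not met at Day 56, and the problem is that no such titre need be drawn. Each reading leaves a difficulty, but they are different difficulties.

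A reader might also infer that footnote h rests on detectability alone, or that the texts part only at falls of 30% or less. Neither is right. Footnote h retests and refers on any fall of more than 30%, and for subjects unprotected at baseline it is the broader rule.

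Finally, the same IgG recovery data suggest that most such deficits would be transient. That is fair and lowers the stakes, although without a Day 84 titre the site cannot tell for a given subject.

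**Conclusion.** The inconsistency is certain from the text. Its consequence depends on the detection limit being below the protective level for the assay used, which the documents do not say. On that assumption, the subjects whom footnote h neither retests nor refers although protection is lost are those with a baseline 1.0 to 1.43 times protective and a fall of 30% or less to a detectable, non-protective Day 56 titre. The window narrows as the baseline rises, and as the detection limit rises above 0.7 times protective.

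Cohort 1 has at most 8 subjects. The number affected cannot be derived, and the window widths above are not probabilities. No planned analysis uses either cut-off, so no trial result is affected. The point is minor: an unresolved conflict between two safety-referral rules.

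**What to change.** In Protocol Table 2 footnote h, and in the SAP copy for consistency, add one limb to the Day 84 retest trigger and to the referral rule: *or, if above the protective level at baseline, is now below the protective level*. Keep the existing detection and 30% limbs so that no current referral is lost. The baseline condition avoids retesting subjects who were never protected and have not fallen.

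The Day 112 retest trigger needs no change. Every subject in the gap has a titre below baseline, so if that persists at Day 84 the existing wording already calls for the Day 112 draw.

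State the same combined referral rule for Cohort 1 in Section 6.7.3, so that the two texts agree. If the detection and protective limits coincide for the assays used, a sentence saying so is enough instead.

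The cost is wording in three places (two copies of footnote h, and 6.7.3) and a few extra titres at visits already scheduled. The ceiling is 8 subjects × 2 antibodies × 2 visits = 32.
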